Biochemistry-A ^b	-14	-	-	-	-	-	-	X	-	-	-	X	X	X	-	-	-	X	X	X	-	
Biochemistry-B ^b	-14	-	-	-	-	-	-	X	-	-	-	-	-	X	-	-	-	-	X	X	-	
Calculated CLcr (Cockcroft and Gault's formula) ^{b, d}	-14	-	-	-	-	-	-	X	-	-	-	X	X	X	-	-	-	X	X	X	-	
Detection of SARS-CoV-2 (COVID-19) by PCR	-14	-	-	-	-	-	-	-	-	-	-	-	-	-	-	-	-	-	-	-	-	
Pregnancy test (serum β-hCG) (only if the patient is a WOCBP)	-14	-	-	-	-	-	-	X	-	-	-	-	-	X	-	-	-	-	X	X	-	
ECG ^e	-14	-	-	-	-	-	-	X	-	-	-	-	-	X	-	-	-	-	-	X	-	
LVEF (by ECHO or MUGA) ^f	-14	-	-	-	-	-	-	-	-	-	-	-	-	-	-	-	-	-	-	X	-	
Randomization ^g	-14	-	-	-	-	-	-	-	-	-	-	-	-	-	-	-	-	-	-	-	-	
Bosentan delivery and patient's diary ^h	-	X	-	-	-	-	-	-	-	-	-	-	-	-	-	-	-	-	-	-	-	
Prophylactic medication ⁱ	-	-	-	-	-	-	-	X	-	-	-	-	-	X	-	-	-	-	X	-	-	
Lurbinectedin 1h (-5/+20 min) infusion	-	-	-	-	-	-	-	X	-	-	-	-	-	X	-	-	-	-	X	-	-	
Bosentan oral administration	-	-	X	X	X	X	X	X ^j	-	-	-	-	-	-	-	-	-	-	-	-	-	
Contact to patients (via telephone or other) ^k	-	-	X	X	X	X	X	-	-	-	-	-	-	-	-	-	-	-	-	-	-	
AAG blood sample collection	-	-	-	-	-	-	-	X	-	-	-	-	-	X	-	-	-	-	-	-	-	
IL6 blood sample collection	-	-	-	-	-	-	-	X	-	-	-	-	-	X	-	-	-	-	-	-	-	

Study Period►	Screening (days prior to registration)	Cycle 1												Cycle 2						Cycle 3	End of Treatment	Follow-up AEs
		-6	-5	-4	-3	-2	-1	1*	2	3	5	8	15	1	2	3	5	8	15			
Cycle Day►																						
PGt blood sample collection (only if written IC given) ¹	-	-	-	-	-	-	-	One blood sample collected at any time during the study, but preferably just before lubrinezdin treatment start in Cycle 1												-	-	
Lurbinectedin PK blood sample collection ^m	-	-	-	-	-	-	-	X	X	X	X	X	-	X	X	X	X	X	-	-	-	-
Bosentan PK blood sample collection ^m	-	-	-	-	-	-	-	X	X	-	-	-	-	-	-	-	-	-	-	-	-	-
AEs ⁿ	Continuous ^o																		X ^p			
Intercurrent events, concomitant disease and therapies	Continuous																		-			

Registration = confirmation of eligibility and inclusion; Day 1 = the day of lubrinezdin administration (with infusion start) of cycle 1 or 2; Day 8 = seven days after the lubrinezdin administration of cycle 1 or 2 (± 2 days); Day 15 = fourteen days after the lubrinezdin administration of cycle 1 or 2 (± 2 days).

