	
Secondary PK parameters: Similar models used for the primary endpoint will be fit to the data with dose-normalized $AUC_{(0-t)}$ and C_{max} and in Cl, V_{ss} and $T_{1/2}$ of lurbinectedin or metabolite to parent exposure PK parameters ratio, as the dependent variable. Results will also be assessed graphically.
 
Plasma protein binding: A similar model used for the primary endpoint will be fit to the data with dose-normalized AUC_u as the dependent variable.
 
Safety: Descriptive statistics will be used to characterize the profiles of drug-related AEs, drug-related deaths, SAEs, clinical laboratory data, drug-related delays and/or treatment discontinuations. All AEs will be graded according to NCI-CTCAE v.5. Tables will be displayed by sequence and treatment (Test or Reference).
 
Pharmacogenetics: Descriptive statistics will be used to summarize pharmacogenetic data at the time of planned analysis.

PLANNED TRIAL PERIODS (individually per patient)
	
Patients will be evaluated at scheduled visits in three study periods:
 
 • Pre-treatment (screening): from signature of the ICF to the day of first administration of the study treatment (bosentan or lurbinectedin). • Treatment: from first administration of the study treatment (bosentan or lurbinectedin) to the last dose of lurbinectedin plus 31 days (end-of-treatment, EOT) (maximum of three cycles). • Follow-up: after EOT, patients with treatment-related toxicities > grade 2 will be followed every four weeks until recovery to at least grade 1 or stabilization of all treatment-emergent AEs, or until the start of a new antitumor therapy, until the continuation of treatment outside this study under a Compassionate Use Agreement or death, whichever occurs first. 
Patients will be considered to be on-study from the signature of the ICF to the end of the follow-up period. Patients will be considered to be on-treatment for the duration of their treatment and until the day of EOT, immediately before the start of the follow-up period.
 
An end-of-treatment (EOT) visit will be performed within 31 days (± 10 days) after administration of the last dose of lurbinectedin, unless the patient dies or starts any new antitumor therapy outside this clinical study, in which case the EOT visit should be performed immediately before the start of the new therapy (ideally the day before or the same day).

[figure not shown]

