5.2.1 Discontinuations

5.2.1.1 Treatment Discontinuation

Treatment discontinuation occurs when an enrolled patient ceases to receive the study treatment regardless of the circumstances. By convention, the date of EOT is defined as 31 days after the day of the last dose of lorbinectedin (treatment discontinuation), the start of a new antitumor therapy or death, whichever occurs first, in which case the date of administration of this new therapy or the date of death will be considered the date of EOT.

The primary reason for any treatment discontinuation will be recorded on the patient's electronic Case Report Form (eCRF).

If a patient discontinues treatment, every effort should be made to complete the scheduled assessments as appropriate.

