6.5 EVALUATIONS AT THE END OF TREATMENT

The end-of-treatment (EOT) visit will be scheduled within 31 days (\pm 10 days) after administration of the last dose of lorbinecetin, unless the patient starts a subsequent antitumor therapy, in which case the end-of-treatment visit should be performed immediately before the start of the new therapy (ideally the day before or the same day).

Patients who meet the continuation criteria and obtain a clear clinical benefit with lorbinecetin after the completion of the first two study cycles, may continue treatment outside this study under a Compassionate Use Agreement after the completion of the optional third study cycle. Should the patient continue under a Compassionate Use Agreement, the treating center must request authorization to the relevant Health Authorities and notify the Sponsor in due time. Patients, regardless of the reason for ending the treatment, will have to undergo at the end of treatment the following assessments:

- Complete physical examination (BSA and height not needed).
- ECOG PS.
- Laboratory tests (hematology and biochemistry A and B, and Calculated CLcr). Calculated CLcr [Cockcroft and Gault's formula] should be provided only if serum creatinine levels are above ULN.
- Coagulation (INR) will be repeated only if clinically indicated.
- ECG (in triplicate) and LVEF assessment.
- Adverse Events.
- Intercurrent events, concomitant disease and therapies.
- Pregnancy test in WOCBP.

Adverse events must be reported for 31 days after the last study treatment administration. All serious adverse events (SAEs) occurring within 31 days of the last study treatment administration or until the start of a new antitumor therapy, until the continuation of treatment outside this study under a Compassionate Use Agreement or death, whichever occurs first, will be reported. Beyond this period of time, only those suspected to be treatment-related SAEs will be reported (Section [8.5.2](#)). The Sponsor will evaluate all safety information that is spontaneously reported by an Investigator beyond the time frame specified in the protocol.

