7.4 CRITERIA FOR TREATMENT CONTINUATION

Patients may continue treatment with lurbinectedin as long as no unacceptable toxicity and/or PD occurred, and for a maximum of three cycles. Thereafter, treatment with lurbinectedin can continue under a Compassionate Use Agreement.

- **Patients assigned to Sequence 1 (TR)** (lurbinectedin + bosentan in Cycle 1), after Cycle 1 the administration of a new cycle should be delayed if the criteria in [Table 7](#) are not met on the corresponding Day 1. Re-assessments will be performed periodically at intervals of at least 72 hours but not more than one week. Lurbinectedin administration should be delayed until recovery of these parameters. A maximum delay of 14 days from the theoretical due date will be allowed for recovery from treatment-related AEs. If recovery has not occurred

after that period, the patient should discontinue the treatment, except in case of obvious patient benefit at the criteria of the Investigator and upon agreement with the Sponsor.

- **Patients assigned to Sequence 2 (RT)** (lurbinectedin + bosentan in Cycle 2), criteria for treatment continuation should be investigated on Day 15 of Cycle 1 in order to confirm bosentan administration start on Day -5 of Cycle 2, assuring that the continuation criteria will be finally met on Day 1 of Cycle 2 assessment. In case of detected abnormalities on Day 15 in sequence RT, these assessments should be repeated every 48-72 hours until recovery to retreatment criteria. Initiation of bosentan will be delayed for a maximum of 14 days to ensure that pre-treatment with bosentan is fulfilled. If recovery has not occurred after that period, the patient should discontinue the treatment, except in case of obvious patient benefit at the criteria of the Investigator and upon agreement with the Sponsor.

Re-treatment criteria for lurbinectedin administration should be met on Day 1 of Cycle 2. If they were not met, treatment will be delayed for a maximum of 2 days to evaluate continuation of lurbinectedin administration, with re-treatment criteria being checked every 24 hours. During this time the patient will continue receiving bosentan. If after 2 days of delay the patient does not meet the criteria for treatment continuation, bosentan will be stopped and the patient will be considered not evaluable for the trial.

If the criteria for treatment continuation are not met as described above, treatment must be discontinued and the EOT visit performed.

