8.5 ADVERSE EVENT REPORTING PROCEDURES

8.5.1 Reporting of Adverse Events

The Sponsor will collect AEs until 31-day (± 10 days) after administration of the last dose of lorbinecetin or until the start of a new antitumor therapy, until the continuation of treatment outside this study under a Compassionate Use Agreement or until the date of death, whichever occurs first. All AEs suspected to be related to the study drug(s)/IMP(s) must be followed-up after the time of therapy discontinuation until the event or its sequelae resolve or stabilize at an acceptable level to the Investigator and the Sponsor.

All AEs, including medication errors and uses outside what is foreseen in the protocol, must be recorded in English using medical terminology in the source document and the

eCRF. Whenever possible, the Investigator will record the main diagnosis instead of the signs and symptoms normally included in the diagnoses.

Investigators must assess severity (grade) of the event following the NCI-CTCAE v.5 and assign a relationship to each study drug(s)/IMP(s); and pursue and obtain information adequate both to determine the outcome and to assess whether it meets the criteria for classification as a SAE requiring immediate notification to the Sponsor or its designated representative. The Investigator must provide any relevant information as requested by the Sponsor in addition to that on the eCRF.

Abnormal laboratory tests occurring during the study must only be recorded in the AE section of the eCRF if the disorder:

- Is associated with clinically significant symptoms, and/or
- Leads to a change in study dosing (omission, delay or reduction) or discontinuation from the study, significant additional concomitant drug treatment or other therapy, and/or
- Leads to any of the outcomes included in the definition of a SAE.

Otherwise, laboratory results should be reported in the corresponding section of the eCRF (e.g. biochemistry, hematology).

Signs and symptoms: The Sponsor will consider signs and symptoms all the events ongoing during the screening period, except for prior history conditions, which should be reported in the medical history form. Ongoing events during the screening period are those present at any time between the informed consent date and the first drug administration, regardless of if they may be resolved or not at the date of Cycle 1 Day 1.

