8.5.2 Reporting of Serious Adverse Events

The Sponsor will collect SAEs from the time of signing of the ICF and until 31 (± 10) days after administration of the last dose of lorbinecetin or until the start of a new antitumor therapy, until the continuation of treatment outside this study under a Compassionate Use Agreement or death, whichever occurred first. Beyond this period of time, only those SAEs suspected to be related to the IMPs will be collected. Nonetheless, the Sponsor must evaluate any safety information related to the clinical study that is spontaneously reported by an Investigator beyond the time frame specified in the protocol.

All SAEs (as defined above) that have occurred after patient registration, regardless of relationship to the study drug(s)/IMP(s), must be reported immediately, and always within 24 hours to the Pharma Mar S.A. Pharmacovigilance Department electronically by completing the applicable eCRF section. Only in situations of electronic system failure or pregnancy exposure during the clinical trial, can SAEs be reported using paper on a “SAE form by fax ([contact]), e-mail ([contact]@pharmamar.com) or telephone ([contact]). Out of office hours [Greenwich Meridian Time (GMT)], assistance on SAE reporting can be obtained by calling the Pharmacovigilance Department at [contact]. In case of electronic system failure or pregnancy exposure during the clinical trial, SAEs

initially reported by alternative methods (not electronically), must be followed by a completed electronic SAE reporting on eCRF from the investigational staff within one working day.

SAEs occurring during the screening phase (from ICF signature to the first study drug administration) and after off-study will be reported using a paper “SAE form” that must be forwarded as mentioned above always within 24 hours to the Pharma Mar S.A. Pharmacovigilance Department by fax or email.

All SAEs suspected to be related to the study drug must be followed until the event or its sequelae resolves or stabilizes to at least grade 1, or to an acceptable level according to the Investigator and the Sponsor or his/her designated representative.

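### The protocol ends AE and SAE collection at two different points: 31 days after the last lurbinectedin dose in most sections, but 31 days after the last study treatment in Section 6.5

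*Protocol*

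**What the plan says.** Both drugs count as study treatment. The treatment period runs "from first administration of the study treatment (bosentan or lurbinectedin) to the last dose of lurbinectedin plus 31 days" (Synopsis, Planned trial periods; repeated in 5.2 and Table 5 footnote d). The other end points compare as follows.

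- **EOT date (5.2.1.1):** "By convention, the date of EOT is defined as 31 days after the day of the last dose of" lurbinectedin, or new antitumor therapy or death if earlier.
- **EOT visit (Synopsis, 5.2, 6.5):** within 31 (±10) days of the last lurbinectedin dose.
- **AE collection (8.5.1):** "The Sponsor will collect AEs until 31-day" (±10 days) after the last lurbinectedin dose.
- **SAE collection (8.5.2):** "The Sponsor will collect SAEs from the time of signing of the ICF and until 31" (±10) days after the last lurbinectedin dose; later SAEs only if suspected to be related to the IMPs.
- **Safety monitoring (3.1, and SAP section 2):** up to 31 (±10) days after the last lurbinectedin infusion. Section 8.3 refers to the last treatment infusion, which can only be lurbinectedin.
- **AE and SAE reporting (6.5):** "Adverse events must be reported for 31 days after the last study treatment administration". The next sentence gives SAEs the same anchor.
- **TEAE definition (9.3.2):** counted from the last treatment dose, with no drug named.

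Section 7.4 describes how a Sequence 2 patient can have bosentan as the last study drug. The start may be late: "Initiation of bosentan will be delayed for a maximum of 14 days to ensure that pre-treatment with bosentan is fulfilled". If the Cycle 2 Day 1 criteria then fail for 2 days, "bosentan will be stopped and the patient will be considered not evaluable for the trial".

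**The concern.** For a patient whose last study drug is lurbinectedin, the two anchors agree. For the Sequence 2 patient stopped after the lead-in, the last lurbinectedin dose was Cycle 1 Day 1, weeks before the last bosentan tablet. A site that follows 8.5.1 and 8.5.2 could then close routine collection soon after the last tablet, or date its close before it. A site that follows 6.5 would continue for 31 days, and 9.3.2 can be read as still counting those events as treatment-emergent. The protocol does not say which rule prevails.

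The loss would be new AEs, and SAEs that the investigator does not suspect to be related. The SAP plans bosentan-related AE and SAE tables and a listing of AEs related only to bosentan (11.2.1, 11.3.1). With eight planned patients, one truncated record is visible in such displays.

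A second gap concerns a Sequence 1 patient who takes bosentan but never receives lurbinectedin. Section 9.1 foresees such patients and plans separate reporting, for example by narrative. The lurbinectedin-based clock never starts for them.

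**Working it through.** This is calendar arithmetic on the protocol's own schedule.

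**Inputs**
- Cycle length 21 days (SAP 7.4). With Cycle 1 infusion = Day 1, Cycle 2 Day 1 = Day 22.
- Lead-in of 5 days, Day -5 to Day -1 (3.1, 7.2).
- Up to 2 further days while the Day 1 criteria are rechecked, with bosentan continuing (7.4).
- Delay of bosentan start, *d* = 0 to 14 days (7.4).
- End of collection: last lurbinectedin dose + 31 days, ±10 in 8.5.1 and 8.5.2.

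**The plan's own figure.** 5 lead-in days + 2 delay days = 7. This reproduces the stated maximum of seven consecutive days before infusion.

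**Formulas** (counting without a Day 0)
- First tablet: Day 22 − 5 + *d* = Day 17 + *d*.
- Last tablet after 7 days: Day 17 + *d* + 6 = Day 23 + *d*.
- Nominal end from Cycle 1 Day 1: Day 1 + 31 = Day 32. Limits: Day 22 (−10) and Day 42 (+10).
- Days of collection after the last tablet: 32 − (23 + *d*) = 9 − *d*.

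| Start delay *d* | Last tablet | Nominal end minus last tablet | At +10 limit (Day 42) | 31 days after last tablet |
|---|---|---|---|---|
| 0 | Day 23 | +9 | +19 | Day 54 |
| 9 | Day 32 | 0 | +10 | Day 63 |
| 10 | Day 33 | −1 | +9 | Day 64 |
| 14 | Day 37 | −5 | +5 | Day 68 |

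At the −10 limit (Day 22), the end falls 1 day before the Day 23 tablet even with no start delay.

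**Sensitivity.** The trial schematic equates Day 15 of Cycle 1 with Day -6 of Cycle 2. That puts each tablet one day earlier, so each gap becomes 10 − *d*: +10 with no delay, 0 at 10 days and −4 at 14 days. The pattern is unchanged.

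**Sequence 1, bosentan only.** With no lurbinectedin dose, the 31-day date in 5.2.1.1, 8.5.1 and 8.5.2 cannot be computed. New antitumor therapy or death can still end collection. Section 6.5 gives 31 days after the last tablet.

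**The case against.** The strongest reply is that the damage is limited and partly retrospective. While a patient takes bosentan for a planned Cycle 2, nobody yet knows that Cycle 1 Day 1 was the last lurbinectedin dose. AE recording is marked continuous in the schedule, and 7.4 requires an EOT visit once the criteria fail. A reader might infer from the negative gaps that collection would lapse during dosing. The documents do not support that: the Day 32 date becomes fixed only once treatment has stopped. What stands is uncertainty about the tail after the last tablet, and an EOT date that can precede it.

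Other stronger readings also fail.
- **That every safety end point runs from lurbinectedin alone.** Sections 6.5 and 9.3.2 do not.
- **That these patients' AEs simply stop being collected.** Related AEs are followed until they resolve or stabilize (8.5.1), related SAEs remain reportable (8.5.2), and 9.3.2 keeps later related or unknown-relationship events as TEAEs.
- **That a bosentan-only patient has no collection end point.** Section 6.5 supplies one.
- **That the tail is shorter still because of a tablet on Day 24 or Day 38.** The Day 1 tablet is tied to an infusion that does not take place here, so such a dose is not clearly provided for.
- **That bosentan's own safety is a stated objective.** The objective is its effect on the safety profile of lurbinectedin, and a patient stopped before the Cycle 2 infusion adds nothing to that comparison.

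The zero and negative nominal gaps also need a Day 15 failure, a start delay of about 9 days or more, recovery and then a second failure. That is uncommon in a trial of eight patients.

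**Conclusion.** The point holds as a conflict between anchors, in a situation that the protocol itself describes. Under 8.5.1 and 8.5.2 as written, the Sequence 2 patient stopped after a 7-day lead-in has about 9 days of routine collection after the last tablet, against 31 under 6.5. With a start delay of about 9 days or more, the nominal end falls at or before the last tablet. At 14 days it falls about 5 days before, or about 5 days after if the full +10 tolerance is used. These figures assume a 21-day cycle and two further bosentan days while Day 1 is rechecked; the schematic's day numbering moves them by one day. The exposure is confined to new AEs and to SAEs not suspected to be related. The conflict should be corrected, but it does not touch the primary PK analysis.

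**What to change.** Reconcile the passages so that the 31 days for AE and SAE collection, the EOT date and the EOT visit all run from the last administration of lurbinectedin or bosentan, whichever is later. Section 6.5 already does this for AE and SAE reporting.

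- Amend the Synopsis, 3.1, 5.2, 5.2.1.1, the EOT-visit sentence in 6.5, Table 5 footnote d, 8.3, 8.5.1 and 8.5.2. Section 8.3 needs its own wording because it refers to an infusion.
- In 9.3.2, state that the last treatment dose means the last dose of either drug.
- Align the safety-monitoring text in SAP section 2.

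This also gives a bosentan-only patient an EOT date and a 31-day window. The cost is an amendment to wording, plus longer collection for the rare patient stopped after the lead-in: to Day 54 instead of Day 32 with no start delay (22 days more), or to Day 68 with a 14-day delay (36 days more). Nothing changes for patients whose last study drug is lurbinectedin.

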*** Permitted windows for assessments before Day 1 of Cycle 1:**

If physical examination, ECOG PS, vital signs, Hematology, Biochemistry-A, Biochemistry-B, CLcr (provided only if serum creatinine levels are above ULN) and Coagulation were assessed >10 days before Day 1 of Cycle 1, the tests must be repeated the day before or the Day 1 (always prior to lubrinezdin infusion).

If pregnancy test was done >7 days before Day 1 of Cycle 1, the test must be repeated the day before or the Day 1 (always prior to lubrinezdin infusion).

A patient should only be treated if eligibility criteria are still met according to assessments performed closest to treatment start.

Permitted windows for assessments after Day 1 of Cycle 1:

A ± 2 -day time window will be allowed for Hematology, Biochemistry-A and CLcr (provided only if serum creatinine levels are above ULN) on Day 8 and Day 15, and for vital signs on Day 8 of Cycle 1.

A -1 day window will be allowed for physical examination, ECOG PS, vital signs, Hematology, Biochemistry-A, and Biochemistry-B, CLcr (provided only if serum creatinine levels are above ULN) and Pregnancy test on Day 1 of Cycle 2 and further cycles (always prior to lubrinezdin infusion).

A $+2$ days window for Day 1 lubrinezdin administration of Cycle 3.

If a drug administration is delayed beyond the permitted protocol window, assessments planned for the original administration day must be repeated on the day the dose is finally administered.

^a Should treatment be administered more than ten days after the screening tests, repeat these tests prior to the first infusion and if clinically indicated. Height needs to be measured at baseline only. BSA will not be reported at the EOT. BSA calculated according to DuBois formula (see [Appendix 4](#)).

^b Any patient having any grade ≥ 3 laboratory abnormalities and/or treatment-related AEs is suggested to have the relevant tests re-assessed at intervals of at least 72 hours but not more than one week until recovery to at least grade 2 has been documented.

^c Repeat during treatment period and at EOT if clinically indicated.

^d Calculated CLcr [Cockcroft and Gault's formula] should be provided only if serum creatinine levels are above ULN.

^e ECG should be done in triplicate (at screening, Day 1 and EOT visit) and allow rhythm definition (at least 30 seconds of duration), PR interval and QT interval (raw and corrected by HR using Bazett's formula). On Day 1, 5 minutes before SOI (-25 to -1 min before preinfusion PK samples collection) and 1 hour after EOI (-15 to -1 min before the PK sample collection), both will be done in triplicate.

^f A previous LVEF assessment could be used if was made within 28 days prior to screening and will be repeated if clinically indicated, and EOT.

^g Randomization apply for all patients.

^h Bosentan for self-administration and the patient's diary should be given to the patient on Day -6 with a $-2/+1$ day time window (i.e., from Day -8 to Day -5).

ⁱ Corticosteroids i.v. (according to institutional standard antiemetic doses, minimum dose of 8 mg/day and maximum dose of 20 mg/day of dexamethasone sodium phosphate or equivalent); If feasible, anti-emetic medication and dose administered in Cycle 1 should be maintained in Cycle 2. Serotonin (5-HT₃) antagonists (ondansetron at least 8 mg i.v. and no more than 16 mg of ondansetron) (i.e., 30 \pm 5 minutes before lubrinezdin administration).

^j If patient does not fulfill inclusion criteria (Cycle 1 in TR sequence) in Day 1 assessments and lubrinezdin administration is postponed no more than two days, bosentan should not be discontinued.

Study Period►	Screening (days prior to registration)	Cycle 1												Cycle 2					Cycle 3	End of Treatment	Follow-up AEs
		-6	-5	-4	-3	-2	-1	1*	2	3	5	8	15	1	2	3	5	8	15		
Cycle Day►																					

^k The study center will contact the patients (via telephone or other methods) to remind them or confirm that they have taken the morning and evening dose of bosentan when they are not at the study center.

^l Blood sample for genotyping will be collected at any time during the study but preferably just before infusion start in Cycle 1, only if written IC for the pharmacogenetic sub-study is given.

^m Serial peripheral venous blood samples for determination of lubinectedin (total and unbound), lubinectedin metabolites (i.e., M1 and M4) and bosentan plasma concentrations will be collected at the time points indicated in Section [8.1.1, Table 9](#).

ⁿ Clinical assessment of the patient's signs and symptoms (including nurses' assessment and patient-reported issues) should continue on an ongoing basis throughout the study and be reported at least every cycle as AEs. Only information on SAEs that occurred after signature of the informed consent and up to Day -5 is required before treatment start. Grading should be as per the NCI-CTCAE v.5. Signs and symptoms will be assessed by the Sponsor as all the events ongoing during the screening period, except for prior history conditions, which should be reported in the medical history form. Ongoing events during the screening period are those present at any time between the informed consent date and the first drug administration, regardless of if they may be resolved or not at the date of Cycle 1 Day 1.

^o The "AE form" will be used only for events that occur after the first drug infusion or any event related to a study procedure within the study period (according to ICH guidelines); and to report 'ongoing' baseline conditions in case of any significant change (improvement or worsening) during the study.

^p Patients will be followed every four weeks until recovery to at least grade 1 or stabilization of all treatment-emergent AEs, or until the start of a new antitumor therapy, until the continuation of treatment outside this study under a Compassionate Use Agreement or death, whichever occurs first.

Hematology: Differential WBC (including neutrophils, monocytes and lymphocytes), erythrocytes, hemoglobin, hematocrit and platelets.

Coagulation: INR.

Biochemistry A: AST, ALT, AP, lactate dehydrogenase (LDH), creatinine, glucose, creatine phosphokinase (CPK), CPK-MB fraction (if CPK is elevated above the normal range) and gamma glutamyltransferase (GGT) and total bilirubin (direct bilirubin if total bilirubin is above the ULN).

Biochemistry B: Serum electrolytes (Na+, K+, Mg++), total calcium, total proteins, albumin, C-reactive protein (CRP).

AAG, alpha-1 acid glycoprotein; AE, adverse events; ALT, alanine aminotransferase; AP, alkaline phosphatase; AST, aspartate aminotransferase; β-hCG, beta subunit of human chorionic gonadotropin; BP, blood pressure; BSA, body surface area; CLcr, Creatinine clearance; CPK, creatine phosphokinase; CPK-MB, creatine phosphokinase-isoenzyme MB; CRP, C-reactive protein; D, day; ECG, electrocardiogram; ECHO, echocardiogram; ECOG PS, Eastern Cooperative Oncology Group Performance Status; EOT, end of treatment; GGT, gamma glutamyltransferase; HR, heart rate; IC, informed consent; ICF, informed consent form; ICH, International Conference on Harmonization; IL6, interleukin 6; INR, International Normalized Ratio; LDH, lactate dehydrogenase; LVEF, left ventricular ejection fraction; min, minutes; MUGA, multiple-gated acquisition scan; NCI-CTCAE, National Cancer Institute Common Toxicity Criteria; PCR, polymerase chain reaction; PGt; Pharmacogenetic; PK, pharmacokinetics; TR, test-reference sequence; SAE, serious adverse event; SARS-CoV-2, Severe acute respiratory syndrome coronavirus 2; SOI, start of infusion; T^a, temperature; ULN, upper limit of normal; WBC, white blood cells; WOCBP, women of childbearing potential.

SEQUENCE 2 (RT):

Study Period►	Screening (days prior to registration)	Cycle 1						Cycle 2									Cycle 3		End of Treatment	Follow-up AEs	
		1*	2	3	5	8	15	-5	-4	-3	-2	-1	1	2	3	5	8	15	1	31 (±10)	
Cycle Day►																					
Lurbinectedin PK blood sample collection ^m	-	X	X	X	X	X	-	-	-	-	-	-	X	X	X	X	X	-	-	-	-
Bosentan PK blood sample collection ^m	-	-	-	-	-	-	-	-	-	-	-	-	X	-	-	-	-	-	-	-	-
AEs ⁿ		Continuous ^o																		X ^p	
Intercurrent events, concomitant disease and therapies		Continuous																		-	

Registration = confirmation of eligibility and inclusion; Day 1 = the day of lurbinectedin administration (with infusion start) of cycle 1 or 2; Day 8 = seven days after the lurbinectedin administration of cycle 1 or 2 (±2 days); Day 15 = fourteen days after the lurbinectedin administration of cycle 1 or 2 (±2 days).

